## **9.8. Concomitant Medications**

Concomitant medications will be coded to the ATC classification using the WHO Drug Dictionary. The use of prior and concomitant medications taken during the study will be recorded on the eCRFs. A by-participant listing of concomitant medication use will be presented ([Listing 16](#)). The use of concomitant medications during the study will be summarized by ATC Level 1, ATC2 Level 2 and treatment group for the Safety population ([Table 98](#)).

## **9.9. Other Safety Measures**

Not applicable.

## **10. PHARMACOKINETICS**

Not applicable.

## 11. IMMUNOGENICITY EVALUATION

All immunogenicity analyses will be performed in the Full Immunogenicity Population and the PP Immunogenicity Population.

### 11.1. Primary Immunogenicity Analyses

There are no primary immunogenicity endpoints.

### 11.2. Secondary Immunogenicity Analyses

The *C. jejuni* capsule-specific IgG serum antibody titers and FR (for post-baseline time points) will be summarized using a geometric mean with 95% CI, minimum, and maximum for each visit and for peak titer by treatment group ([Table 15](#) for the Full Immunogenicity Population and [Table 16](#) for the PP Immunogenicity Population); the percentage of responders with 95% CI will also be presented for post-baseline time points.

Graphical presentations of immune response by treatment group will include reverse cumulative distribution curves ([Figure 2](#) for the Full Immunogenicity Population and [Figure 3](#) for the PP Immunogenicity Population) and longitudinal presentation of GMTs with 95% CI ([Figure 12](#) for the Full Immunogenicity Population and [Figure 13](#) for the PP Immunogenicity Population).

### 11.3. Exploratory Immunogenicity Analyses

The CRM197-specific IgG serum antibody titers and FR (for post-baseline time points) will be summarized using a geometric mean with 95% CI, minimum, and maximum for each visit and for peak titer by treatment group ([Table 17](#) for the Full Immunogenicity Population and [Table 18](#) for the PP Immunogenicity Population); the percentage of responders with 95% CI will also be presented for post-baseline time points.

Analogous tables summarizing titers, FR, and responders by visit and treatment group will be presented for *C. jejuni* capsule-specific IgG ALS ([Table 19](#) for the Full Immunogenicity Population and [Table 20](#) for the PP Immunogenicity Population), *C. jejuni* capsule-specific IgM serum antibodies ([Table 21](#) for the Full Immunogenicity Population and [Table 22](#) for the PP Immunogenicity Population), and CRM197-specific IgM serum antibodies ([Table 23](#) for the Full Immunogenicity Population and [Table 24](#) for the PP Immunogenicity Population).

Graphical presentations of immune response by treatment group and time point will include reverse cumulative distribution curves ([Figure 4](#), [Figure 5](#), [Figure 6](#), [Figure 7](#), [Figure 8](#), [Figure 9](#), [Figure 10](#), and [Figure 11](#)) and longitudinal presentation of GMTs with 95% CI ([Figure 14](#), [Figure 15](#), [Figure 16](#), [Figure 17](#), [Figure 18](#), [Figure 19](#), [Figure 20](#), and [Figure 21](#)).

### 11.4. Additional Immunogenicity Analyses

A listing of all individual immunogenicity results will be presented by treatment group, participant ID, planned time point, and actual study day in [Listing 8](#).

The timing of the maximum titer result for each participant will be summarized by immune response and treatment group ([Table 25](#) for the Full Immunogenicity Population and [Table 26](#) for the PP Immunogenicity Population). If a participant has more than 1 time point at their maximum value, they will be classified using the earlier time point.

Dose verification assays performed during the study showed that some study product preparations did not fall within the acceptable range of the target dose of CJC2V. The dose verification assays were performed on three aliquots of the prepared study product (except for the sentinels in Cohort 3 which only had one aliquot tested), so the results are only specific to the preparation (denoted by date of preparation) and not individual participants. Thus, the average of all aliquots tested from a preparation will be used as an estimate of the dose that all participants who were vaccinated on the day of the preparation received. The estimated dose received (based on the dose verification assay) will be summarized by vaccination and treatment group (i.e., the planned dose and study product) for the Safety Population ([Table 27](#)).

To assess the relationship between estimated dose received (based on the dose verification assay results) and immune response, a set of correlation analyses will be performed. For each immune response and vaccination, the spearman correlation between the cumulative estimated dose of CJC2V received and the maximum immune response titer measured for that cumulative dose will be calculated for all participants receiving CJC2V alone across all cohorts (i.e., regardless of the planned CJC2V dose) and for all participants receiving CJC2V+ALFQ across all cohorts (i.e., regardless of the planned CJC2V dose) for each immune response in both the Full Immunogenicity Population ([Table 28](#)) and the PP Immunogenicity Population ([Table 29](#)).

The immune responses that will be analyzed are *C. jejuni* capsule-specific IgG ALS antibody titer, *C. jejuni* capsule-specific IgG serum antibody titer, CRM197-specific IgG serum antibody titer, *C. jejuni* capsule-specific IgM serum antibody titer, and CRM197-specific IgM serum antibody titer. Because the ALS assay is only performed once between each vaccination, the correlation will use the immune response measured 7 days post the applicable vaccination (Study Days 8, 36, and 64 for each vaccination respectively). The correlations involving the serum immune responses will use the maximum titer measured at Day 8 or 29 for Vaccination 1, Study Day 36 or 57 for Vaccination 2, and Study Day 64, 85, or 113 for Vaccination 3. In alignment with the analysis population definitions, if a participant does not receive a third vaccination, their available data will still be included in the “Vaccination 3” panels for the Full Immunogenicity Population but not for the PP Immunogenicity Population.

A scatterplot of the cumulative dose received and *C. jejuni* capsule-specific IgG ALS antibody titer with Spearman correlation coefficient and 95% CI will be presented by vaccination and ALFQ status ([Figure 22](#) for the Full Immunogenicity Population and [Figure 23](#) for the PP Immunogenicity Population). Analogous figures will be presented for the remaining immune responses for the Full Immunogenicity Population ([Figure 24](#), [Figure 26](#), [Figure 28](#), and [Figure 30](#)) and the PP Immunogenicity Population ([Figure 25](#), [Figure 27](#), [Figure 29](#), and [Figure 31](#)). The two-sided 95% CI will be calculated using Fisher’s Z-transformation.

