6. Participation in a previous *Campylobacter* study or reports having received vaccination against *Campylobacter* within the last 3 years.
7. History of microbiologically confirmed *Campylobacter* infection in the last 3 years.
8. Occupation involving handling of *Campylobacter* bacteria or vaccine products currently or in the past 3 years.
9. Use of immunosuppressive/immunomodulating disease therapy within 90 days
10. Received Ig or other blood products (with exception of Rho D Ig) within 90 days prior to enrollment.
11. Have a history of severe reactions following previous immunization with any licensed or unlicensed vaccine.
12. Known hypersensitivity to any components of vaccine, adjuvant, or diluent.
13. Received or plan to receive a licensed live vaccine within 30 days prior to 1st vaccination and to 30 days after the last vaccination.
14. Received or plan to receive a licensed, inactivated, vaccine within 14 days prior to 1st vaccination to 14 days after the last vaccination, or a seasonal influenza and/or COVID-19 vaccine \pm 7 days from study product vaccination.
15. Individuals in whom the ability to observe possible local reactions at the eligible injection sites (deltoid region) is unacceptably obscured due to a physical condition or permanent body art.
16. Within 14 days prior to vaccination has received an oral or parenteral (including intra-articular) corticosteroid of any dose for 5 or more days, or high-dose inhaled corticosteroids.
 - a. High dose defined per age as using inhaled high dose per reference chart (https://www.nhlbi.nih.gov/files/docs/guidelines/asthma_qrg.pdf)
17. Current or history of alcohol or drug abuse within one year prior to enrollment.

18. Have any diagnosis, current or past, of schizophrenia, bipolar disease, or other psychiatric diagnosis that may interfere with subject compliance or safety evaluations.
19. Have been hospitalized for psychiatric illness, history of suicide attempt, or confinement for danger to self or others within one year prior to enrollment.
20. Are pregnant, breastfeeding, or plan to become pregnant or breastfeed at any given time during the study.
21. Have an acute illness as determined by study clinician licensed to make medical diagnoses and listed on the Form FDA 1572 as the site PI or sub-investigator, within 72 hours prior to enrollment.

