6.2.2.1 Laboratory Specimen Preparation, Handling, and Storage

Biosamples (serum, stools, and PBMCs) for immunological assays will be collected, processed, cryopreserved, and stored as detailed in the protocol MOP. All immunological assays will be performed in batches after all samples have been collected for a given assay within a cohort.

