### 3.3. Study Definitions and Derived Variables

Unless otherwise specified, the baseline value will be defined as the last value obtained prior to the first vaccination. Vital signs assessed on Day 1 prior to study vaccination will be considered as baseline. Any medical condition that is present at the time that the participant is screened will be considered as baseline and will only be reported as an AE if symptoms related to the condition occur with greater frequency and/or severity after vaccination during the AE reporting period.

Change from baseline is defined as the additive change from baseline, i.e.,  $CHG_{ij} = y_{ij} - y_{i0}$  where  $y_{ij}$  is the measurement for participant  $i$  at time point  $j$  and  $y_{i0}$  is the measurement for participant  $i$  at baseline (prior to vaccination 1).

Fold-rise (FR) from baseline is defined as the multiplicative change from baseline, i.e.,  $FR_{ij} = \frac{y_{ij}}{y_{i0}}$  where  $y_{ij}$  is the response for participant  $i$  at time point  $j$  and  $y_{i0}$  is the response for participant  $i$  at baseline (pre-vaccination 1). Individual FR values will be reported to 1 decimal place.

The peak titer and peak fold-rise are defined as the maximum value for a participant at any time after the first vaccination.

A responder is defined as having  $\geq 4$ -fold increase relative to baseline, i.e.,  $FR_{ij} \geq 4$  for participant  $i$  at post-baseline time point  $j$ . For serum assays, participants are classified as responders or not at Days 8, 29, 36, 57, 64, 85, and 113; for the ALS assay, participants are classified as responders or not at Days 8, 36, and 64.

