## 4.3. Selection of Study Population

Cohort 1 was enrolled under protocol v4.0 (25MAY2022), and Cohorts 2 and 3 were enrolled under protocol v6.0 (08MAY2023); the full list of inclusion and exclusion criteria can be found in the specified versions of the protocol. The inclusion and exclusion criteria were updated between the enrollment of Cohort 1 and Cohort 2 to be less restrictive. The major differences are listed below:

- The inclusion criteria in v4.0 required a Body Mass Index (BMI) < 36; this was changed to BMI < 40 in v6.0.
- The exclusion criteria in v4.0 excluded participants with “documented family history of auto-immune conditions”; this was changed to “documented history of auto-immune conditions in a first-degree relative” in v6.0.
- The exclusion criteria in v4.0 excluded participants with “travel to countries with high *Campylobacter* rates (to include Asia, Africa, and Central and South America) within two years prior to dosing.” This exclusion criterion was removed in v6.0.

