#### 6.3.2. Full Immunogenicity Population

The Full Immunogenicity Population consists of all participants who received any study product and contributed both pre- and at least one post-study vaccination blood samples for immunogenicity testing for which valid results were reported. Participants will be analyzed according to actual study product received.

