## 6.5. Missing Data

All attempts will be made to collect all data per protocol. As missing data are expected to be minimal, no imputation will be performed for missing values. Any data point that appears to be erroneous or inexplicable based on clinical judgment will be investigated as a possible outlier. If data points are identified as outliers, sensitivity analyses will be performed to examine the impact of including or excluding the outliers. Any substantive differences in these analyses will be reported.

All immunogenicity variables have a lower limit of quantification (LLOQ). Results that are <LLOQ will be imputed as the limit of detection (LOD) in calculations of summary statistics in tabular and graphical displays. The CRM197-specific IgG and IgM assays have a 3-fold titration series, so the imputed value will be  $LOD = 1/3 * LLOQ$ . The *C. jejuni* capsule-specific serum IgG and IgM and ALS IgG assays have a 2-fold titration series, so the imputed value will be  $LOD = 1/2 * LLOQ$ . Imputed values will be rounded to the nearest whole number for consistency with conversion of results from  $\log_{10}$  titer to titer. The number of results <LLOQ will be reported in tabular summaries.

Immune Response	LLOQ		
	Log 10 Titer	Titer	Imputed Titer when <LLOQ
C. Jejuni Capsule-specific IgG Serum Antibody	2.30	200	100
C. Jejuni Capsule-specific IgM Serum Antibody	2.30	200	100
CRM 197 -specific IgG Serum Antibody	3.00	1000	333
CRM 197 -specific IgM Serum Antibody	2.00	100	33
C. Jejuni Capsule-specific IgG ALS Antibody	0.70	5	3

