*[Implementation Note: All valid results included in the applicable analysis population will be considered (i.e., results from visits that are excluded from the PP Immunogenicity Population will not be considered for the PP Immunogenicity Population).]*

Immune Response	Statistic	Vaccination 1 a		Vaccination 2 b		Vaccination 3 c	
		CJCV2 (N=X)	CJCV2+ALFQ (N=X)	CJCV2 (N=X)	CJCV2+ALFQ (N=X)	CJCV2 (N=X)	CJCV2+ALFQ (N=X)
C. jejuni Capsule-specific IgG Serum Antibody	n	x	x	x	x	x	x
	Spearman Correlation Coefficient	x.XXX	x.XXX	x.XXX	x.XXX	x.XXX	x.XXX
	95% CI d	x.XXX, x.XXX	x.XXX, x.XXX	x.XXX, x.XXX	x.XXX, x.XXX	x.XXX, x.XXX	x.XXX, x.XXX
CRM 197 -specific Capsule-specific IgG Serum Antibody	n	x	x	x	x	x	x
	Spearman Correlation Coefficient	x.XXX	x.XXX	x.XXX	x.XXX	x.XXX	x.XXX
	95% CI d	x.XXX, x.XXX	x.XXX, x.XXX	x.XXX, x.XXX	x.XXX, x.XXX	x.XXX, x.XXX	x.XXX, x.XXX
C. jejuni Capsule-specific IgG ALS	n	x	x	x	x	x	x
	Spearman Correlation Coefficient	x.XXX	x.XXX	x.XXX	x.XXX	x.XXX	x.XXX
	95% CI d	x.XXX, x.XXX	x.XXX, x.XXX	x.XXX, x.XXX	x.XXX, x.XXX	x.XXX, x.XXX	x.XXX, x.XXX
C. jejuni Capsule-specific IgM Serum Antibody	n	x	x	x	x	x	x
	Spearman Correlation Coefficient	x.XXX	x.XXX	x.XXX	x.XXX	x.XXX	x.XXX
	95% CI d	x.XXX, x.XXX	x.XXX, x.XXX	x.XXX, x.XXX	x.XXX, x.XXX	x.XXX, x.XXX	x.XXX, x.XXX
CRM 197 -specific Capsule-specific IgM Serum Antibody	n	x	x	x	x	x	x
	Spearman Correlation Coefficient	x.XXX	x.XXX	x.XXX	x.XXX	x.XXX	x.XXX
	95% CI d	x.XXX, x.XXX	x.XXX, x.XXX	x.XXX, x.XXX	x.XXX, x.XXX	x.XXX, x.XXX	x.XXX, x.XXX

Notes: N = Number of participants with at least one visit post the specified vaccination visit in the Full Immunogenicity Population summed across all cohorts by ALFQ status; n = Number of participants in the Full Immunogenicity Population with valid immunogenicity results included in the correlation.

a Results are from Study Day 8 for the ALS assay and the maximum result from Study Days 8 and 29 for serum assays.

b Results are from Study Day 36 for the ALS assay and the maximum result from Study Days 36 and 57 for serum assays.

c Results are from Study Day 64 for the ALS assay and the maximum result from Study Days 64, 85, and 113 for serum assays.

d 95% confidence interval calculated using Fisher's Z transformation.

Table with a similar format:

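### SAP 11.4 correlates estimated dose with raw titer across sequential cohorts without the Day 1 titer; add a fold-rise sensitivity row and a footnote that dose is aligned with cohort

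*SAP*

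**What the plan says.** - **The analysis.** SAP 11.4 sets out "the spearman correlation between the cumulative estimated dose of CJC2V received and the maximum immune response titer measured for that cumulative dose" for five immune responses, after each of three vaccinations, separately for CJCV2 alone and CJCV2+ALFQ. Serum results are the maximum over Days 8 and 29, Days 36 and 57, or Days 64, 85 and 113. ALS uses Days 8, 36 and 64. Day 1 enters none of these windows.
- **Pooling.** The Table 28 notes count participants "summed across all cohorts by ALFQ status". They otherwise cover n, the visits used and the Fisher-Z interval.
- **Origin.** SAP 11.4 reports that some preparations fell outside the acceptable range of the target dose. SAP 15 says the correlations were added once those results were known, before lock and unblinding. No other planned analysis relates estimated dose to response.
- **Cohorts.** Dose is fixed by cohort at 1, 3 and 10 µg (SAP 4.4.5), and each cohort starts only after the previous one's Day 64 safety review (SAP 4.1). SAP 4.3 says Cohort 1 enrolled under protocol v4.0 and Cohorts 2 and 3 under v6.0, with looser eligibility. Of the travel exclusion it says: "This exclusion criterion was removed in v6.0".
- **Assays.** Protocol 6.2.2.1: "All immunological assays will be performed in batches after all samples have been collected for a given assay within a cohort".
- **Fold-rise.** SAP 3.3: "Fold-rise (FR) from baseline is defined as the multiplicative change from baseline". It is tabulated in Tables 15–24 but not in Tables 28–29.
- **Low results.** SAP 6.5: "Results that are <LLOQ will be imputed as the limit of detection (LOD) in calculations of summary statistics in tabular and graphical displays".

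**The concern.** Planned doses are 3-fold and 3.3-fold apart. Unless preparations missed target by about that much, ranking participants by estimated dose ranks them by cohort. Anything that differs between cohorts then enters the coefficient as if it were dose. A systematic difference between assay runs is one such thing, if runs follow cohorts. The SAP already defines a quantity that is less sensitive to it, and this analysis leaves it out.

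Tables 28–29 will print 5 responses × 3 vaccinations × 2 ALFQ strata × 2 populations = 60 coefficients with CIs. A reader could take an interval excluding 0 as dose response when it reflects the assay run. A reader could also take a flat coefficient as absence of dose response when a shift masks one.

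**Working it through.** **Inputs from the documents.** Planned n is 30 per ALFQ stratum, 10 per cohort (protocol 9.3.1). Doses are 1, 3 and 10 µg. The interval is Fisher-Z (SAP 11.4). The LLOQ/imputed titers in SAP 6.5 reproduce: 200/2 = 100, 1000/3 = 333, 100/3 = 33, 5/2 = 2.5, rounded to 3. SAP 11.4 gives no expected correlation to reproduce.

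**Assumed, because the documents give none.** Day 1 SD 0.35 log10; response mean 0.3 and SD 0.4 log10; baseline fully carried into the post-vaccination titer; about 3% of Cohort 1 baselines below LLOQ; preparation log-SD 0.15; five preparations per cohort; assay shift of 0, half and full size in Cohorts 1, 2 and 3.

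**When the CI excludes 0.** With standard error 1/√(n−3) = 1/√27 = 0.192, this needs |rho| > tanh(1.96 × 0.192) = 0.36.

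**A 2-fold Cohort 1-to-3 shift, no dose effect (hand check).**
- Cohort offsets are 0, 0.15 and 0.30 log10, with SD 0.15 × √(2/3) = 0.123.
- Raw titer variance within cohort is 0.35² + 0.4² = 0.2825.
- The induced linear correlation is 0.123/√(0.015 + 0.2825) ≈ 0.225. The simulated Spearman mean is 0.21.
- With atanh(0.21) = 0.213, the share of CIs excluding 0 is about P(Z > (0.377 − 0.213)/0.192) = P(Z > 0.85) ≈ 20%.
- For fold-rise, an assay factor k cancels: kT/kB = T/B. If Day 1 is below LLOQ, B is a constant and k remains.

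**Simulation, 8,000 trials per scenario** (% of 95% CIs excluding 0):

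| Scenario | Raw titer | Fold-rise |
|---|---|---|
| No dose effect, no shift | 5 | 5 |
| Assay shift 1.25-fold | 7 | 5 |
| Assay shift 1.5-fold | 10 | 5 |
| Assay shift 2-fold, up or down | 19–21 | 5 |
| Assay shift 3-fold | 43 | 5 |
| 2-fold, SDs 0.2/0.3 | 39 | 5 |
| 2-fold, SDs 0.6/0.8 | 9 | 5 |
| 2-fold, 60–65% of Day 1 below LLOQ | 18–21 | 5–8 |
| 2-fold, 85–87% of Day 1 below LLOQ | 17–21 | 10–15 |
| 2-fold difference in responsiveness, no assay shift | 20 | 32 |

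At 96% of Day 1 results below LLOQ, a 2-fold shift gives 20% raw and 18% fold-rise, which is almost no correction.

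**Hiding a real slope.** Take 0.3 log10 per 10-fold dose. Dose effects are 0, 0.3 × log10(3) = 0.14, and 0.30. A 2-fold downward shift subtracts 0, 0.15 and 0.30, leaving almost nothing. Raw titer then detects the slope in 5% of trials, against 22–34% with no shift. Fold-rise detects it in 22–35%, depending on baseline carry-over, but in only 16% with 66% of baselines below LLOQ and 7% with 88%.

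**Why fold-rise does worse under a responsiveness difference.** The offset sits only in the post-vaccination titer, and the fold-rise SD is smaller (0.4): 0.123/√(0.015 + 0.16) ≈ 0.29, against 0.225 for raw titer.

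**A within-cohort correlation as the alternative.** It holds at 5% under both kinds of shift. It detects the 0.3 slope in only 5–7% of trials at preparation log-SD 0.05–0.3, and 10% at 0.5, so it is no usable substitute.

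**The case against.** **Protocol 6.2.2.1 does not settle how assays were run.** A reader might infer from it that each cohort was assayed separately and that a shift exists. The sentence says when assays may start. It does not rule out cohorts sharing a run, and no interim immunogenicity review forces cohort-by-cohort testing. Details sit in the MOP, which may cover bridging. This stands, so the premise is conditional.

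**A shift could already be looked for.** Tables 15–24 give Day 1 GMTs and fold-rise by planned group. The reverse cumulative plots include Day 1, the time-trend figures are paneled by cohort, the scatterplots mark cohort, and Listing 8 gives every titer. This also stands, but the printed coefficient and interval stay uncorrected and the alignment goes unstated.

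**The limitation belongs to sequential escalation generally.** True, and maximum titer is a legitimate secondary endpoint. Tables 28–29 are nonetheless where estimated dose and response are reduced to one number across cohorts.

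**Fold-rise is not neutral.** It is weak when Day 1 is mostly below LLOQ, and worse than raw titer under a responsiveness difference. This stands, and it limits fold-rise to a sensitivity row.

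**Stakes are low.** SAP 6.8 plans no testing, no decision rule uses the coefficient, and at a 2-fold shift about 80% of raw CIs still cover 0. This fixes the weight of the point.

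**Eligibility.** A reader might infer that dropping the travel exclusion raised baseline antibody in Cohorts 2 and 3. The documents do not show this. The v6.0 criteria still exclude "History of microbiologically confirmed *Campylobacter* infection in the last 3 years", together with recent *Campylobacter* study participation, vaccination or occupational handling. It is the weaker route.

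**Conclusion.** A low-cost improvement to consider. The text establishes that the dose correlation uses raw titer, pools sequential non-randomized cohorts, omits Day 1 and carries no caveat. It does not establish that assays were run by cohort, that a shift occurred, or that any coefficient will be wrong.

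If runs did follow cohorts, a 2-fold Cohort 1-to-3 shift with no dose effect would take the share of raw-titer CIs excluding 0 from 5% to about 20%. That figure ranges from 9% to 39% over the titer SDs tried. Fold-rise stays near 5% only while Day 1 is mostly measurable. It would be wrong to conclude that fold-rise simply divides the problem out, or that it should replace the raw-titer correlation. The footnote is warranted by the sequential enrollment and the eligibility change alone, whatever the assay arrangement turns out to be.

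**What to change.** 1. Keep the raw-titer correlations and the plots in Figures 22–31.
2. In Tables 28–29 add one sensitivity row per response: the Spearman correlation, with Fisher-Z 95% CI, of cumulative estimated dose with maximum titer in the window divided by Day 1 titer. Use participants with a valid Day 1 result for that assay. Give that n and the number of Day 1 results below LLOQ in each ALFQ stratum. The separate n is needed because the Full Immunogenicity Population requires participants who "contributed both pre- and at least one post-study vaccination blood samples for immunogenicity testing for which valid results were reported", which does not guarantee a Day 1 result for every assay.
3. Confirm from the MOP or laboratory records how assay runs related to cohorts and whether common controls were used.
4. Add this footnote to the tables and figures: *Estimated dose is closely aligned with cohort; cohorts were enrolled sequentially, were not randomized against each other, and eligibility changed after Cohort 1 [add, if confirmed: and assays were run in separate batches by cohort]. Fold-rise reduces a cohort-level assay shift only where Day 1 is at or above LLOQ and does not remove cohort differences in responsiveness. No coefficient alone establishes dose response.*

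**Cost.** SAP wording and a few lines of code on data already collected, with no new samples or assays. The 60 coefficients become 120. Fold-rise can itself mislead if baseline does not carry into the post-vaccination titer. Assuming prior exposure adds 0.6 log10 to baseline in 20–40% of Cohorts 2 and 3 without carrying over, 8–17% of fold-rise CIs exclude 0 with no dose effect, against 5% for raw titer.
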